Treatment of the DM and associated complications, dosing of the insulin, change from PO to insulin treatment and back to PO medications during hospitalization or at discharge will be guided by the admitting team with as needed help from the inpatient Endocrinology Consultation Service.

Decisions about insulin dosing or other medication use designed to treat hyper or hypoglycemia episodes or underlying diabetes mellitus will be made based on hospital POC blood glucose meters and not based on CGM readings alone.

Patients will be asked to give the research team “provider access” to their cloud CGM software, or to allow the team to download their CGM data prior to discharge if their reading devices do not automatically synchronize with the cloud software.

CGM data will be compared with POC blood glucose monitoring obtained in the hospital. Different patient variables (demographics, comorbidities, labs and vitals, administered medications) will be collected from electronic health record and will be evaluated to determine if they would interfere with CGM readings. The accuracy of CGM for glucose measurement in the hospital will be calculated.

Outcomes measured:

CGM accuracy when compared with POC monitors.

CGM accuracy at detection of hypo or hyperglycemia episodes when compared with POC monitors.

Number of CGM alarms and the clinical result of these alarms: nurse notification, treatment of hypo or hyperglycemia episodes, treatment for rapid declining glucose alarms.

Materials:

CGMs (sensors, transmitters and readers) belong to patients

Provider access to cloud CGM program will be granted to the research team by the patient.

Personnel:

A research assistant that will identify the patients and enroll them into the study.

Subject Information

Target accrual is the proposed total number of subjects to be included in this study at Mayo Clinic. A “Subject” may include medical records, images, or specimens generated at Mayo Clinic and/or received from external sources.

Target accrual: 150

Subject population (children, adults, groups): Admitted adult medical and surgical patients with Diabetes Mellitus type I or II that have their own CGM monitor present on admission or able to be placed after admission.

Inclusion Criteria:

Patients with Type 1 or 2 Diabetes Mellitus,

Patients 18 years of age or older,

Patients admitted under medical or surgical services.

Patients treated with diet alone, insulin (SQ, insulin pump) or oral hypoglycemic medications.

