The study will use data that have been collected under another IRB protocol. Include in the Methods section and enter the IRB number from which the research material will be obtained. *When appropriate, note when subjects have provided consent for future use of their data and/or specimens as described in this protocol.*

Enter one IRB number per line, add more lines as needed

Data Specimens Data & Specimens _____

Data Specimens Data & Specimens _____

Data Specimens Data & Specimens _____

Data Analysis

Power analyses may not be appropriate if this is a feasibility or pilot study, but end-point analysis plans are always appropriate even if only exploratory. Provide all information requested below, or provide justification if not including all of the information.

Power Statement:

Data Analysis Plan:

Data will be described as percentages or means. Pearson χ^2 and Kruskal Wallis tests will be used to compare categorical and continuous variables respectively. Odds ratios, 95% confidence intervals and p-values will be reported for each model. All tests of significance will be 2-sided and the level of statistical significance will be set at p-value < 0.05.

Mean Absolute Relative Differences will be calculated between matched pairs of POC monitors and the closest CGM reading (within 5 minutes of POC). Additionally, level of agreement between the two devices will be examined with Bland-Altman plots, with particular attention focused on detection agreement in range (70-180 g/dl). Poisson or negative binomial regression will be utilized to assess count variables such as number of alarms, nurse notification, and hypo or hyperglycemia events adjusting for patient characteristics. Finally, longitudinal analysis will be conducted to determine differences associated with medications, clinical parameters or diagnosis. Analysis will seek to define if there are any differences between CGM and POC measurement based on these changes.

Endpoints

Primary: CGM accuracy - mean absolute relative difference (MARD)

Secondary:

- CGM accuracy at detection of hypo or hyperglycemia episodes when compared with POC monitors. (MARD for readings <70g/dl, >180g/dl, >250g/dl)
- CGM accuracy for detecting time in range (70-180 g/dl MARD).
- Number of CGM alarms and the clinical result of these alarms: nurse notification, treatment of hypo or hyperglycemia episodes, treatment for rapid declining glucose alarms.

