- Time in therapeutic range for glucose as measured by CGM and POC glucose monitor.
- Detection of medications, clinical parameters or diagnoses that would interfere with CGM reading.
- Effect of CGM use on length of hospital stay, post-surgical duration of hospitalization

Clinical safety measures:

- Number of sensors with failure.
- Number of sensors removed for procedure.
- Number of sensor related skin reaction (contact dermatitis, infection)

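### The endpoint on factors interfering with CGM is analysed only through the CGM–POC difference, which cannot show which device a factor disturbed

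*Combined protocol and SAP*

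**What the plan says.** The secondary endpoints in the Endpoints section include "Detection of medications, clinical parameters or diagnoses that would interfere with CGM reading". The Methods prepare for this: "Different patient variables (demographics, comorbidities, labs and vitals, administered medications) will be collected from electronic health record", and these variables "will be evaluated to determine if they would interfere with CGM readings". Both sentences assign the effect to the CGM.

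The comparator is the hospital meter: "CGM data will be compared with POC blood glucose monitoring obtained in the hospital". In the Data Analysis Plan, "longitudinal analysis will be conducted to determine differences associated with medications, clinical parameters or diagnosis", followed by "Analysis will seek to define if there are any differences between CGM and POC measurement based on these changes". The outcome variable and model form are not given. The MARD pairs contain the same two devices: "Mean Absolute Relative Differences will be calculated between matched pairs of POC monitors and the closest CGM reading (within 5 minutes of POC"). The Bland-Altman analysis also uses only these two.

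No laboratory, venous or plasma glucose is designated as a reference. Laboratory data appear only among the candidate interfering variables. Nothing in the plan analyses meter error, removes pairs in which the meter may be affected, or says how a CGM–POC difference is to be assigned to one device. The Methods also have patients calibrate the sensors that need it from hospital POC values.

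**The concern.** The endpoint makes a statement about one named device, but the analysis measures a contrast between two. Laboratory values, vital signs, drugs and comorbidities could in principle act on either. If a factor acts on the meter, the meter's error varies with the very factor being tested, so it biases that factor's coefficient and does not merely add noise to MARD. Restating the accuracy hypothesis as agreement with POC would not cure this, because the endpoint would still name CGM as the device disturbed.

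What is at stake is the list of interferents that the trial reports. The Methods base treatment decisions on POC readings, so a meter effect reported as a sensor effect would draw attention away from the device on which those decisions rest.

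**Working it through.** The documents give no device-error, effect-size or power figure for this endpoint (the power statement is blank), so there is no stated result to reproduce. The check is whether the planned data can identify the affected device.

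**1. Identifiability.** Let G be true glucose, CGM = G(1+c) and POC = G(1+p). The relative difference in a pair is

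(CGM − POC)/POC = (1+c)/(1+p) − 1.

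G cancels, and only the ratio of the two error terms remains. For example:
- p = −0.10, c = 0: 1/0.90 − 1 = +11.1%.
- p = 0, c = +0.111: 1.111/1 − 1 = +11.1%.
- p = c = +0.10: 1.10/1.10 − 1 = 0%.

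The first two cases look the same, and the third looks like no effect. Neither more patients nor a longitudinal model separates c from p.

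**2. The same with random error.** Simulation of 400,000 pairs. All inputs are assumed and none comes from the documents: log-normal glucose with median 165, random CV 5% for POC and 10% for CGM.

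| Case | Mean CGM–POC difference | MARD | CGM bias against truth | POC bias against truth |
|---|---|---|---|---|
| No bias | +0.3% | 8.9% | 0.0% | 0.0% |
| POC −10% | +11.5% | 13.9% | 0.0% | −10.0% |
| CGM +11.1% | +11.4% | 13.2% | +11.1% | 0.0% |
| Both +10% | +0.2% | 8.1% | +10.0% | +10.0% |

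POC biases of −5% and −15% give +5.6% and +18.1%; matching CGM biases of +5.3% and +17.6% give +5.5% and +17.9%. The small MARD gaps follow from the assumed error structure and offer no usable way to tell the cases apart. The last two columns separate the cases, but they need a third reference.

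**3. Would a meter-only shift be detected?** From the documents: 150 patients, two-sided 0.05. Assumed: factor present in 20% (30 against 120 patients), 12 CGM–POC pairs per patient, within-patient SD 12 points, between-patient SD 6 or 10 points, t-test on patient means.

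SD of a patient mean = √(SD_between² + 12²/12): √48 = 6.93 or √112 = 10.58.

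SE = SD × √(1/30 + 1/120) = SD × 0.204: 1.41 or 2.16.

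For shifts of 3, 5 and 8 points in the difference, shift/SE is 2.12 or 1.39, 3.54 or 2.31, and 5.66 or 3.70. With a non-central t on 148 degrees of freedom, the flag rates are 28–56%, 63–94% and 96–100%. This is simply the power to see a shift of that size; it says nothing about how likely such a shift is.

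**4. Power of a laboratory check.** Same assumptions, with 3 CGM–laboratory pairs per patient.

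SD = √(36 + 144/3) = 9.17 or √(100 + 48) = 12.17; SE = 1.87 or 2.48.

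A true CGM shift of 5 points: 5/SE = 2.67 or 2.01, power 52–76%. A shift of 3 points: 1.60 or 1.21, power 23–36%.

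**5. Calibrated sensors.** If a sensor took on the whole meter error p through calibration, CGM = G(1+p). The CGM–POC difference would then be 0 and CGM minus laboratory would show p. With p = −10%, the planned analysis would miss the factor and the laboratory check would blame the sensor.

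**The case against.** The best reply is that this is mostly a matter of wording. The analysis sentence itself is neutral about the device. The comparator is declared openly in Aim 1, and the Background presents POC testing as the current standard of care. This is one of several secondary endpoints in a minimal-risk observational study, and a reworded endpoint would remove the overclaim. That stands, and it is why rewording is the core of the fix. It does not remove the gap: two sections still promise a finding about CGM that the planned data cannot deliver.

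A second reply is that the flag rates rest wholly on assumed inputs. A shift placed in POC alone must appear in the difference. That also stands, and the rates serve only as an illustration.

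A third is that a laboratory check has costs: lower power, uncertain availability of time-matched values, and the calibration route shown above. Those points stand and shape the fix.

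A reader might infer more than the documents support: that meter interferents *will* be reported as CGM interferents, that factors not flagged will be declared safe, or that hospitals would stop CGM on the strength of the list. No section says that any drug, laboratory value or condition disturbs the hospital meter. The endpoint is about detection and makes no promise to certify safety. Nothing in the documents describes how hospitals would use the list.

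**Conclusion.** The point holds as one of identifiability. As written, the plan cannot answer its own interference endpoint, because the CGM–POC difference does not show which device moved. Misattribution of a meter effect to CGM, and masking of an effect common to both devices, are possible outcomes; neither is shown to occur.

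The identifiability result needs only that device error can depend on the factor. The size of the problem cannot be taken from the documents. On the assumptions above, a meter-only shift of 5 points would be flagged in 63–94% of trials of 150 patients, if such a factor existed and were present in 20% of them. The primary endpoint is a separate question. This is worth correcting before analysis, since it changes what the trial may conclude at little cost.

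**What to change.** 1. Reword the secondary endpoint, and the matching sentence in the Methods, to *factors associated with the CGM–POC difference (device not identified)*. This alone removes the overclaim.
2. If the laboratory data already being collected include glucose results (an assumption) that can be paired with a CGM reading under the 5-minute rule, add to the Data Analysis Plan a secondary comparison of CGM minus laboratory glucose. Run it for all candidate factors: a check limited to those flagged against POC would never reach a factor that shifts both devices alike.
3. Report that comparison separately for sensors calibrated from hospital POC readings and for those that are not, because meter error can pass into the former.
4. Attribute a factor to CGM only when this comparison supports it. Label a non-significant laboratory result *device not identified*, not evidence that CGM is unaffected.

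Cost: revised wording and one further model per candidate factor on record data, with no extra blood draws or patients. The downside is power: about 52–76% for a true 5-point CGM shift on the assumed inputs, and less once split by calibration. Some factors will stay unattributed. If too few laboratory pairs exist, step 1 still applies.

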Continuous Glucose Monitoring in Hospitalized Patients With Diabetes Mellitus

NCT#04653454

12August2020

IRB Minimal Risk Protocol Template

Note: If this study establishes a human specimen repository (biobank) for research purposes, do not use this template. Use the Mayo Clinic Human Specimen Repository Protocol Template found on the IRB home page under Forms and Procedures at

[REDACTED]

First-time Use: Use this template to describe your study for a new IRB submission.

1. Complete the questions that apply to your study.
2. Save an electronic copy of this protocol for future revisions.
3. When completing your IRBe application, you will be asked to upload this document to the protocol section.

Modification: To modify this document after your study has been approved:

1. Open your study in IRBe. Click on the study 'Documents' tab and select the most recent version of the protocol. Save it to your files.
2. Open the saved document and activate "Track Changes".
3. Revise the protocol template to reflect the modification points, save the template to your files
4. Create an IRBe Modification for the study and upload the revised protocol template.

General Study Information

Principal Investigator: [name].

Study Title: CGM use in hospitalized patients with diabetes mellitus.

Protocol version number and date: Version 1.0, 8/12/2020

Research Question and Aims

Hypothesis: Patient's own CGM (continuous glucose monitor) used in the hospital will be as accurate as POC (point of care) glucose monitors and acknowledgement by providers of high and low glucose trends will prevent episodes of hyper and hypoglycemia.

Aims, purpose, or objectives:

1. To determine if patient's own CGMs worn in the non-ICU hospital setting have adequate accuracy for blood glucose monitoring when compared to point-of-care capillary glucose measurement.
2. To determine if alerts given by CGMs worn in the non-ICU hospital would prevent episodes of hyperglycemia and hypoglycemia.

Background (*Include relevant experience, gaps in current knowledge, preliminary data, etc.*):

Diabetes Mellitus (DM) affects approximately 34.2 million (10.5%) Americans. Hyperglycemia and hypoglycemia in hospitalized patients have been associated with unfavorable clinical outcomes, including higher rates of sepsis, deconditioning, mortality and longer hospital stay. Untreated

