hypoglycemia may lead to neurological damage, cognitive decline, seizures and coma. Additionally, the management of the diabetic complications doubles the inpatient cost per capita compared to non-diabetic patients.

Current standard of care in the hospital recommended by the national guidelines is the bedside point-of-care (POC) glucose capillary testing performed before meals and at bedtime. This approach however does not provide continuous 24-h glucose measurement and fails to detect nocturnal or asymptomatic hypoglycemia or hyperglycemia, all of which are common insulin therapy complications.

Continuous Glucose Monitoring (CGM) represents an alternative with the potential to assist making personalized therapy decisions. It measures levels of interstitial glucose every 5-15 min, which provides better assessment of nocturnal or asymptomatic hypoglycemia or hyperglycemia and shows glycemic patterns following treatment interventions. The ability to monitor glucose more frequently will also allow for timely interventions, and thus hyperglycemia and hypoglycemia episodes can be reduced. There have been studies demonstrating improved glycemic control in insulin-treated DM patients using CGM in outpatient setting, and even a few studies describing the use of CGM in non-ICU hospitalized patients.

Prospective studies evaluating the use of the newer CGMs in non-critically ill hospitalized patients are lacking. The aim of our study therefore was to compare the accuracy of patient's own CGM monitor worn in the hospital in detecting blood glucose levels by comparing them with those measured by a POC blood glucose capillary test.

Study Design and Methods

Methods: *Describe in lay terms, completely detailing the research activities that will be conducted by Mayo Clinic staff under this protocol.*

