All patients admitted to the hospital in inpatient or observation status and having a CGM monitor attached will be screened and identified by providers and nurses. An order will be placed by providers to continue patient's home CGM monitor use in the hospital. A CGM patient agreement describing the hospital policy for use of CGMs will be provided to the patient for signature. (see attached agreement) Patients will be encouraged to continue to wear their CGMs in the hospital unless their presence interferes with patients' medical care. CGM presence will be recorded by nursing in patient chart under LDA (lines, drains, airway) section. A daily report will be run and these patients identified. Patients will be approached by research staff and asked to be enrolled in the study. A research consent will be reviewed with the patients and will be provided to patients for signature. Patients will be asked to continue to use their home CGMs in the hospital. If the sensor will reach the end of life patients have the option to place a new sensor and follow manufacturer recommendations for calibration and setting. Patients are responsible to provide their own sensors, transmitters, readers during the hospitalization period. If it is determined that the current sensor will interfere with the in-hospital medical and surgical care (MRI testing, procedure at the site, etc.), patient will be asked by their providers to remove the sensor and transmitter. Patients will have the option to replace the sensor after the procedure if they so desire. Patients will continue to monitor their glucose via CGM and their approved devices. For flash sensors, patients will be asked to scan their sensor at least every 8 and as needed. CGMs that require calibration will be calibrated by patients using hospital POC glucose meter readings. .

Patients alerted by their CGM about low glucose levels or fast downward or upward trending will be asked to notify their nursing staff. A POC blood glucose check will be done by nursing staff to confirm the alert or the trend. Treatment decisions will be made based on POC readings.

During hospitalization patients will continue to have their blood glucose checked with POC glucose monitor per hospital policy.

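### Length of stay is listed as an effect of wearing a CGM, but no group without CGM and no analysis are defined for it; the prevention claim also has no reference

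*Combined protocol and SAP*

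**What the plan says.** **Stay.** The last item in the list of secondary endpoints is "Effect of CGM use on length of hospital stay, post-surgical duration of hospitalization".

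**Prevention.** Under Research Question and Aims, Aim 2 is "To determine if alerts given by CGMs worn in the non-ICU hospital would prevent episodes of hyperglycemia and hypoglycemia". The second half of the hypothesis says that "acknowledgement by providers of high and low glucose trends will prevent episodes of hyper and hypoglycemia".

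**Who is studied.** Screening under Study Design and Methods starts from inpatients and observation patients with a CGM attached. Subject Information describes adults with their own CGM, either on at admission or placed later, with a target accrual of 150. Stays shorter than 24 h are excluded.

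**What happens to them.** All are asked to keep using their device, under one alert procedure: "Patients alerted by their CGM about low glucose levels or fast downward or upward trending will be asked to notify their nursing staff". Nursing then does a POC check.

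**What is compared.** The Methods state: "CGM data will be compared with POC blood glucose monitoring obtained in the hospital". Patient variables are also examined, but for interference with CGM readings. The Background gives the study aim as the accuracy of the patient's own monitor "worn in the hospital in detecting blood glucose levels by comparing them with those measured by a POC blood glucose capillary test".

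**What is analysed.** The Data Analysis Plan has a general rule that data are summarised by percentages or means, followed by several tests and models. It does not mention length of stay.

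**The concern.** An effect of CGM use on stay is a difference between stay with CGM and stay without it. A claim that alerts prevent episodes is a difference between episode rates with and without the alert, or with and without its acknowledgement. A cohort of wearers under one alert procedure supplies one side of each difference.

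If the plan is followed as worded, either these questions go unanswered or the report draws a causal conclusion that the data cannot carry. Enrolling more patients would not help, because what is missing is a contrast and not precision.

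**Working it through.** The plan gives no figure to reproduce here, so the check sets its sections against each other.

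**Step 1. What each claim needs and what the plan supplies.**

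| Claim | Contrast needed | Supplied in Methods, Subject Information or Data Analysis Plan |
|---|---|---|
| Effect on stay (secondary endpoint) | Mean stay with CGM minus mean stay without CGM | CGM wearers only; no group without CGM defined |
| Prevention (Aim 2 and second half of hypothesis, one claim stated twice) | Episode rate with alerts or acknowledgement, against the rate without | One alert procedure for all; no reference defined |

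As designed, 150 subjects have a CGM and 0 do not. The second term of the stay difference therefore has no data. POC is a comparator for the measurement, within the same patients, and not for the use of the device.

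**Step 2. Whether the Data Analysis Plan fills the gap.**
- Percentages and means: would describe stay, but estimate no effect.
- Chi-square and Kruskal-Wallis tests, and odds ratios: no groups are named.
- Mean absolute relative difference (MARD) and Bland-Altman plots: device agreement.
- Poisson or negative binomial regression: counts of alarms, notifications and glucose events, adjusted for patient characteristics, with no term for CGM use, alert or acknowledgement.
- Longitudinal analysis: differences by medication, clinical parameter or diagnosis, aimed at CGM-POC discrepancy.

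Analyses that name stay: 0. The template text above this plan asks for endpoint analyses even when they are exploratory, or for a justification where information is left out.

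**Step 3. Endpoint and outcome counts.** The six secondary endpoints are accuracy at episodes, accuracy within the target range, alarms and their results, time in range by device, interference, and stay (3 + 3 = 6 across the page break). One of the six, stay, is worded as an effect. The list of outcomes in the Methods has three items, beginning with "CGM accuracy when compared with POC monitors". None is stay. The third covers alarms and the response to them, including treatment when glucose is falling fast. It touches preventive action but does not estimate prevention.

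**Step 4. Why alarm counts do not show prevention.** Suppose an alarm is followed by no episode. The alarm may have been false, glucose may have recovered unaided, routine POC testing may have caught the problem, or the alert may have helped. Without a reference rate these cannot be told apart.

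**Step 5. Whether a contrast exists within the cohort.** Exposure does vary: sensors can be removed for procedures ("Patients will have the option to replace the sensor after the procedure if they so desire"), sensors can fail, some are placed after admission, and some alarms may not reach nursing. None of these is specified as a contrast for stay or prevention. They are also open to confounding. For example, a longer admission gives a sensor more time to fail or be removed, so the association with stay could run from stay to exposure.

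**The case against.** **Aim 2 is phrased conditionally.** It can be read as asking whether alerts come early enough for action, and the chain of alert, notification, POC check and treatment puts that reading into practice. This stands in part. A reader might infer that Aim 2 has no usable endpoint. The documents do not support that, since the alarm endpoint is descriptive and answerable. What remains is that the hypothesis asserts prevention outright and nothing in the plan estimates it.

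**Historical controls may have been intended.** The records section gives a window from 01/01/2010 to 01/01/2022 and pre-printed options on existing data. The tick boxes are not legible, so a reader cannot infer that no comparator was ever intended. What can be said is that the Methods describe no such cohort, matching or adjustment.

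**The inclusion list does not itself require a CGM.** True, but the population statement and the screening text describe CGM wearers, and no other group appears.

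**The general descriptive rule already covers stay.** It does, for description. It does not support the word effect.

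**Within-cohort contrasts could be used.** A reader might infer that every such contrast is necessarily confounded. The documents do not show that. They show only that none is specified.

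**This is one secondary endpoint in a minimal-risk observational study.** Correct, and that limits the weight of the point.

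**Conclusion.** The point holds for the stay endpoint: one of six secondary endpoints is worded as an effect, with no group without CGM and no analysis named for it. It holds as a secondary wording point for the prevention claim, which appears in one of the two aims and in half of the hypothesis and has no reference condition.

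This rests on the text of the Methods, Subject Information, Data Analysis and Endpoints sections and on no assumed inputs. The one uncertainty is the illegible tick boxes in the records section. They bear on what may have been intended, not on what the Methods define.

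A reader might go further and conclude that the study as a whole is undermined. The documents do not support that: the primary MARD endpoint compares CGM with POC readings in the same patients and needs no group without CGM. The matter should be fixed, because the present wording promises conclusions that the design cannot deliver and the correction is small.

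**What to change.** 1. **Stay endpoint.** Reword it as length of hospital stay and post-surgical stay, described in CGM wearers hospitalized for at least 24 h, using the plan's existing descriptive rule and making no claim of effect.
2. **Aim 2 and the matching half of the hypothesis.** Restate both as describing alarms and what follows them: POC confirmation, nurse notification and treatment. This matches the alarm endpoint already in the plan.
3. **Within-cohort comparisons.** State that any comparison by sensor removed or failed, or by alarm notified or not, is exploratory, open to confounding and not evidence of effect.

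**Cost.** No new patients, procedures, data or models. The stated claim becomes weaker, and one aim and part of the hypothesis are rewritten. If the study is already approved, the template's own instructions call for an IRB modification.

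**If the sponsor keeps the causal wording,** the Methods would have to define a comparator (who, from which part of the records window, with the same 24 h minimum stay and other applicable exclusions), and the Data Analysis Plan would need a confounding-adjusted analysis. That is a larger change, requires comparator data, leaves residual confounding possible, and is not part of the inexpensive fix.
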